[name], [name], Center for Digestive Diseases, Karolinska University Hospital

[name], MD, Center for Digestive Diseases, Karolinska University Hospital

[name], MD, The surgical clinic, Stockholm South General Hospital

1:5 Report access to necessary resources during the project

Responsible for the safety of the research participants at each recruiting site:

[name], Head of Function Allied Health Professionals, Karolinska University Hospital

[name], Head of Center for Digestive Diseases, Karolinska University Hospital

[name], Head of the surgical clinic, Stockholm South General Hospital

1:6 Applications to additional authorities

NA

2. Information regarding the project

2:1 Summary of the research project

Shorter length of stay in hospitals can be a problem for older people with multiple comorbidities and functional limitations. Therefore, these patients need to be optimally prepared so that they can regain health and functional capacity as soon as possible after a planned hospital stay e.g. undergoing surgery. The aims of the project are to investigate and identify older people at high risk for complications, as well as evaluate if preoperative physical exercise can decrease the risk of complications, mortality, and prolonged length of stay in hospital after abdominal- and thoracic surgery. The observational study will include patients over the age of 70 years scheduled for surgery at Karolinska University Hospital and Stockholm South General Hospital. The association between preoperative physical activity and function and postoperative complications and length of stay will be investigated. The results from this study will form the basis for the inclusion criteria and power calculation for a randomized controlled intervention study where preoperative home-based exercise will be compared to standard preoperative care. Effects on physical function, quality of life, length of stay, complications and mortality will be studied.

2:2 Which/What scientific research questions form the basis of the project?

Observational study

Which factors can predict complications, length of stay in hospital, and mortality after abdominal and thoracic surgery, and identify older people at high risk?

Intervention study

Can preoperative exercise prior to abdominal- and thoracic surgery decrease the risk of functional decline, postoperative complications, and shorten length of stay in older people at high risk?

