The study is a randomized controlled study where the participants will be randomized to an intervention consisting of preoperative physical exercise or a control group following standard preoperative care. The responsible researcher will perform the randomization. The assessors of physical performance will be blinded to group allocation during the study. This is made possible, as the randomization will be conducted after the baseline assessments. The participants will also receive written information not to reveal their group allocation at follow-up assessments. The intervention period will differ depending on individual variations in preoperative waiting time, but the intervention time will be a minimum of two weeks. To optimize compliance to and quality of the exercise, the intervention will be conducted by a physiotherapist in the participants' home. The results from the observational study will form the basis for possible stratification variables in the intervention study.

Intervention group

The participants will perform individually tailored functional strength training and aerobic training, as well as inspiratory muscle training starting from 30% of maximal inspiratory capacity. On none supervised days the participants will be encouraged to follow recommendations of 30 min physical activity on moderate intensity, and inspiratory muscle training at 20% of maximal capacity. The participants will also receive usual preoperative information.

Control group

The control group will receive usual preoperative information and be encouraged to follow recommendations of 30 min physical activity on moderate intensity at least 5 days/week. Both groups will receive usual postoperative treatment and rehabilitation.

Measurements

At baseline age, sex, comorbidities, smoking habits and living situation will be collected from the medical records. The following measurements will be conducted before the intervention, after the intervention but before surgery, and at discharge from the hospital:

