Six-minute walk, gait speed, chair stands, inspiratory muscle strength, lung function, and grip strength. Mortality, length of stay, discharge destination, postoperative complications (pneumonia, stroke, wound infections, pain etc), and comorbidities will be documented after 30 days and 90 days post surgery. Need of oxygen supplement and respiratory support, and saturation will be retained from the medical records. Data from medical records will be collected after approval from the head of the unit according to laws and regulations. Possible complications or adverse events related to testing or training will be documented.

At baseline and 6 month after surgery the participants will fill in three questionnaires (sent by mail) including activities in daily living (ADL-staircase), physical activity level (PASE), and health-related quality of life (EORTC QLQ-C30). All instrument are validated and frequently used in research both nationally and internationally. Reference values from the Swedish population are to be found for the EORTC QLQ-C30.

If the study results in positive findings with decreased length of stay and improved health-related quality of life, calculations regarding health economics will be performed where the costs of preoperative exercise are put in relations to decreased length of stay.

Statistical analyses

Continuous data will be described with mean and standard deviations, and ordinal data with median and interquartile range (q1-q3). Analyses between groups will be performed with intention-to-treat (ITT) analyses and with Repeated measure ANOVA for continuous normally distributed data and Wilcoxon/Kruskal-Wallis test for ordinal data and continuous skewed data. Analyses will be performed in SPSS.

2:5 Report whether collected biological material will be stored in a bio bank

NA

2:6 Documentation, data protection and archiving

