3:1 How will the selection of research participants be made?

Observational study

Patients referred to the participating clinics will be informed, orally and in writing, about the study and asked for participation by a research or contact nurse at the first visit in the surgical office.

Inclusion criteria: >70 years of age, understand and speak the Swedish language.

Exclusion criteria: Health status that contradicts physical tests of muscle strength, endurance and functional performance, or a need of acute surgery.

Intervention study

Patients referred to the participating clinics will be consecutively asked for participation in the study by a research or contact nurse at the first visit in the surgical office. For more information see below 3.1 heading Observational study.

Inclusion criteria: >70 years of age, understand and speak the Swedish language. Other inclusion criteria will be based on the results from the observational study.

Exclusion criteria: Health status that contradicts physical tests of muscle strength, endurance and functional performance, or a need of acute surgery within 7 days.

3:2 State the relationship between the researchers/test assessors and the research participants

Therapist (e.g. physician, psychologist, physiotherapist) – research participant (e.g. patient, client)

3:3 Describe the statistical basis for the sample size

For the observational study 200 participants will be recruited, based on experiences from previously published studies with similar research questions.

Power for the intervention study will be calculated based on data from the observational study. A previous study calculated power based on a 10% reduction in postoperative complications. For an 80% ($p=.05$) power, a total of 584 patients (292 per group) were to be recruited.

3:4 Is it possible that the research participants will be included in several studies at the same time or close to this time period? If so, which type of research?

The study participants will not be included in other exercise studies, however there are several medical research projects (e.g examination of surgical tissue) ongoing in parallel to this study at the participating sites. The research group will make sure that the research participants do not have a higher cumulative risk at participation.

3:5 What insurance cover the research participants?

The patient insurance legislation covers potential adverse events.

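### Neither standard arm test of the three-visit repeated-measures ANOVA isolates the arm difference at discharge, so neither by itself answers the functional-decline question

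*Protocol*

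**What the plan says.** Protocol 2:2 puts the question for the intervention study as: "Can preoperative exercise prior to abdominal- and thoracic surgery decrease the risk of functional decline"; complications and length of stay follow in the same sentence. The summary in 2:1 gives the rationale that older patients should "regain health and functional capacity as soon as possible after a planned hospital stay".

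Under 2:4, Intervention study, Measurements, the physical measures ("Six-minute walk, gait speed, chair stands, inspiratory muscle strength, lung function, and grip strength") are taken "before the intervention, after the intervention but before surgery, and at discharge from the hospital". Discharge is the only one of these three visits that falls after the operation.

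The Statistical analyses paragraph for the intervention study then states: "Analyses between groups will be performed with intention-to-treat (ITT) analyses and with Repeated measure ANOVA for continuous normally distributed data". Ordinal and skewed data go to rank tests. The paragraph does not say which ANOVA term decides, which visit decides, or whether a follow-up contrast is planned.

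**The concern.** A two-arm, three-visit repeated-measures ANOVA offers two standard tests that involve arm. The group-by-time test has the null that the two mean profiles are parallel over all three visits. The group main effect has the null that the three-visit averages are equal. Neither null is that the arms have the same function at discharge, given baseline.

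The gap matters here because the pre-surgery visit comes straight after strength, aerobic and inspiratory training, and several of the outcomes measure those same capacities. An arm difference at that visit is what the programme is meant to produce. Whether it survives the operation is the open question. If it does not, the exercise arm falls more steeply from pre-surgery to discharge, yet the group-by-time test can still be significant and could be taken as protection against decline. If the main effect is used instead, a real discharge benefit is averaged with baseline, where randomisation implies no difference, and with the pre-surgery visit.

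The point holds with complete data and balanced baselines. It does not depend on dropout.

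**Working it through.** **No figure of the plan's own to reproduce.** The protocol gives no sample size or power for the physical-function analysis. The 584 (292 per group) in 3:3 belongs to a previous study and concerns complications: "A previous study calculated power based on a 10% reduction in postoperative complications". It has no bearing on this point and is used below only as a large sample size.

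**Inputs from the protocol.** Two equal arms (2:7) and three visits (2:4). Significance level 0.05 (3:3, quoted for the previous study; two-sided assumed). Sample sizes for illustration: 40 per arm (amendment, part 3, derived for nutrient variables) and 292 per arm (3:3).

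**Assumed, because the protocol gives none.** SD 1 at every visit, equal correlation r between visits of 0.5 or 0.7 (0.8 as a check), complete data, arm difference d of 0.3 or 0.5 SD.

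**Step 1: group-by-time test.** Let D1, D2, D3 be the true arm differences at the three visits and D̄ their mean. With n per arm, the F test has 2 and 2(2n−2) degrees of freedom and noncentrality

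λ = n Σ(Dt − D̄)² / [2(1−r)].

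- Gain lost by discharge (0, d, 0): Σ = (1/9 + 4/9 + 1/9)d² = 2d²/3.
- Benefit at discharge only (0, 0, d): Σ = 2d²/3.
- Benefit at both later visits (0, d, d): Σ = (4/9 + 1/9 + 1/9)d² = 2d²/3.

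All three patterns give λ = n d² / [3(1−r)]. Under these assumptions the test rejects equally often for each, so its p-value cannot tell a lost gain from a lasting benefit.

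| n per arm | d | r | λ | Rejection rate |
|---|---|---|---|---|
| 40 | 0.3 | 0.5 | 40×0.09/1.5 = 2.4 | 26% |
| 40 | 0.3 | 0.7 | 40×0.09/0.9 = 4.0 | 41% |
| 40 | 0.5 | 0.5 | 40×0.25/1.5 = 6.7 | 62% |
| 40 | 0.5 | 0.7 | 40×0.25/0.9 = 11.1 | 85% |
| 292 | 0.3 | 0.5 | 292×0.09/1.5 = 17.5 | 97% |

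At r = 0.8 and 40 per arm the rates are about 58% (0.3 SD) and 96% (0.5 SD).

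**Step 2: group main effect.** The estimate is D̄, with standard error √[2(1+2r)/(3n)]. At n = 40 this is 0.183 (r = 0.5) or 0.200 (r = 0.7).

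- 0.5 SD at discharge only: D̄ = 0.167, ratio to standard error 0.91 or 0.83, power 15% or 13%.
- 0.5 SD at both later visits: D̄ = 0.333, ratio 1.83 or 1.67, power 44% or 38%.
- Gain lost by discharge: D̄ is the same as for discharge only, so this term rejects in about 8% of trials (0.3 SD) or 13-15% (0.5 SD).

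At 292 per arm, 0.5 SD at both visits gives power above 99%.

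**Step 3: baseline-adjusted contrast at discharge.** The standard error is about √[2(1−r²)/n]. At n = 40 this is 0.194 (r = 0.5) or 0.160 (r = 0.7).

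- Gain lost by discharge: D3 = 0 and the pre-surgery visit does not enter, so the test rejects at its nominal 5%.
- True 0.5 SD at discharge: ratio 2.58 or 3.13, power 72% or 87%, against 62% or 85% for group-by-time.

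**Check.** Simulation of 4,000 trials per setting at 40 per arm agrees. For a lost gain the group-by-time test rejected in 27% and 41% (0.3 SD) and 62% and 85% (0.5 SD), and the adjusted discharge contrast in about 5%. With no effect at any visit, every test rejected in about 5%.

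**The case against.** The strongest reply is that the protocol contains no faulty decision rule. It names a model family and does not say that a significant omnibus result counts as success. A reader might infer that the plan treats any arm difference over time as proof of less decline; the text does not say so. The statistical analysis plan is not shown and may name a contrast, and the discharge contrast can be drawn from the same model and data. This stands as a limit on the criticism. It does not remove it: the only method stated for these measures has two standard arm tests, and neither matches the question.

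Second, the question in 2:2 mentions neither surgery nor a visit as the reference for decline, and 2:1 lists effects on physical function more broadly. For that broader aim a pre-surgery gain is a genuine effect. This also stands. Discharge relative to baseline is a reading supported by the recovery rationale, and change from pre-surgery to discharge is another possible one. On that second reading a lost gain means more decline in the exercise arm, so the omnibus test serves it no better.

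Third, visit means by arm, if reported, would reveal a vanished gain. That reduces the risk of misreading but leaves the formal test unmatched.

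Fourth, it is tempting to say that a lost gain will still give a significant result. At 40 per arm the figures support only that it can. Likewise, the 13-15% power of the main effect applies only to a discharge-only benefit, an unlikely pattern if training raises pre-surgery function.

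Finally, ADL-staircase and PASE are collected at baseline and six months. With two time points, a group-by-time test is already a one-degree-of-freedom change contrast, so the point does not reach these questionnaires.

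**Conclusion.** The concern holds in limited form. For the normally distributed three-visit measures, the stated method leaves the functional-decline question without a matching test, whichever standard arm term is used. The group-by-time test can signal an effect that is gone by discharge, and the group main effect dilutes one that is present there. The discharge contrast avoids both and, at 40 per arm with r of 0.5 to 0.7, has equal or better power for a true discharge benefit.

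The size is illustrative. It rests on assumed effects, correlations, equal variances and complete data, and neither 40 nor 292 per arm is this trial's sample size for function. It also rests on reading decline as function at discharge relative to baseline. This is an inexpensive improvement to the analysis wording. It is not evidence that the trial will reach a wrong conclusion.

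**What to change.** In Protocol 2:4, Intervention study, Statistical analyses, add for the measures taken at three visits:

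- The conclusion on functional decline rests on the one-degree-of-freedom arm contrast at discharge, adjusted for baseline.
- The arm contrast at the pre-surgery visit is reported separately, as the effect of training on preoperative capacity.
- A significant group-by-time or overall group effect is not by itself evidence on functional decline.

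Both contrasts can come from one model fitted to the data already planned. The six-month questionnaires need no change. The cost is wording only, with no added visits, data or patients. The one thing given up is that a purely preoperative gain no longer counts as a positive result on functional decline.

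### For ordinal and skewed trial outcomes that have a baseline, the protocol names a rank test that takes no baseline covariate: valid, but less precise than it need be (minor)

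*Protocol*

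**What the plan says.** The statistical paragraph for the intervention study (Protocol 2:4) divides outcomes by type. Normally distributed continuous outcomes get a repeated-measures method: "Analyses between groups will be performed with intention-to-treat (ITT) analyses and with Repeated measure ANOVA for continuous normally distributed data". Everything ordinal or skewed gets the "Wilcoxon/Kruskal-Wallis test for ordinal data and continuous skewed data". The paragraph does not say whether the tested quantity is the follow-up value or the change, and it states no baseline adjustment.

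The Measurements part of the same section shows which outcomes have a baseline:

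- **Physical function** (six-minute walk, gait speed, chair stands, inspiratory strength, lung function, grip): "The following measurements will be conducted before the intervention, after the intervention but before surgery, and at discharge from the hospital".
- **Questionnaires** (ADL-staircase, PASE, EORTC QLQ-C30): "At baseline and 6 month after surgery the participants will fill in three questionnaires".
- **Clinical outcomes**: "Mortality, length of stay, discharge destination, postoperative complications (pneumonia, stroke, wound infections, pain etc), and comorbidities will be documented after 30 days and 90 days". Of these, mortality, length of stay, discharge destination and postoperative complications have no baseline value.

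Randomisation takes place after the baseline assessments. Stratification is left open: "The results from the observational study will form the basis for possible stratification variables in the intervention study".

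**The concern.** With two arms, the Kruskal-Wallis test is in effect the Wilcoxon rank-sum test. It uses one number per patient and has no place for a covariate. Reading Wilcoxon as the signed-rank test does not help, because that test compares visits within an arm and the sentence is about comparisons between groups.

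So two outcomes from the same patients on the same schedule are treated differently. A normally distributed one gets a method that uses the repeated values. A skewed or ordinal one gets a test that, applied to follow-up values, ignores a baseline already on file. Any chance imbalance at baseline stays in the comparison, and the result is a p-value without a baseline-adjusted effect estimate.

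Functional decline is part of the research question (2:2), and improved quality of life is one of the findings that would trigger the health-economic analysis (2:4). Some of the outcomes likely to fall under the rank rule therefore carry weight.

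**Working it through.** **The plan's own figures.** The protocol gives no power, effect size or baseline correlation for any ordinal or skewed outcome. Its one figure for alpha and power is borrowed (3:3): "A previous study calculated power based on a 10% reduction in postoperative complications", with 292 per group. The control rate is missing, so this cannot be reproduced from the text alone. An assumed fall from 30% to 20%, two-sided 5%, 80% power, gives

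n = [1.960·√(2·0.25·0.75) + 0.842·√(0.3·0.7 + 0.2·0.8)]² / 0.10² ≈ 294 per arm,

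which is close to 292. That calculation is for a binary complication endpoint and has no bearing on this point.

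**Inputs, all assumed.** Two-sided alpha 0.05. Power 80% when follow-up values alone are tested. Correlation ρ between baseline and follow-up of 0.3, 0.5 or 0.7. Equal variances at both visits.

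**Formula.** With follow-up SD set to 1, the SD that matters is 1 for follow-up only, √(1−ρ²) with baseline adjustment and √(2(1−ρ)) for a change score. Follow-up only at 80% power has a standardised effect of 1.960 + 0.842 = 2.802, so

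power = Φ(2.802 / SD − 1.960).

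For example, at ρ = 0.5 with adjustment: 2.802 / 0.866 − 1.960 = 1.275, and Φ(1.275) = 89.9%.

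| ρ | Follow-up only | Baseline-adjusted | Gain (points) | Change score |
|---|---|---|---|---|
| 0.3 | 80.0% | 83.6% | 3.6 | 65.8% |
| 0.5 | 80.0% | 89.9% | 9.9 | 80.0% |
| 0.7 | 80.0% | 97.5% | 17.5 | 95.1% |

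Once the starting power is fixed, the sample size drops out. At ρ = 0.5 other starting powers move as follows: 50% to 61.9%, 70% to 81.8%, 90% to 96.3%. As a sample-size ratio, 1/(1−ρ²) is 1.10, 1.33 and 1.96 at the three correlations.

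**Simulation with rank methods.** The formula is for normal data, so it was checked with rank tests on a skewed (log-normal) and a five-category ordinal outcome. The sizes are 40 and 292 per arm, the two that the protocol mentions, with latent shifts of 2.802·√(2/n) = 0.626 and 0.232 SD. There were 6,000 and 3,000 simulated trials per setting.

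| Outcome, n per arm | ρ | Rank-sum, follow-up | Rank-sum, change | Rank ANCOVA |
|---|---|---|---|---|
| Skewed, 40 | 0.3 | 77.3% | 62.9% | 80.2% |
| | 0.5 | 75.6% | 75.7% | 85.6% |
| | 0.7 | 77.0% | 92.7% | 95.4% |
| Ordinal, 40 | 0.3 | 74.1% | 56.4% | 77.0% |
| | 0.5 | 74.1% | 68.6% | 83.0% |
| | 0.7 | 74.2% | 84.5% | 92.6% |
| Skewed, 292 | 0.3 | 78.0% | 59.6% | 80.8% |
| | 0.5 | 78.1% | 74.4% | 87.5% |
| | 0.7 | 77.7% | 91.8% | 95.8% |
| Ordinal, 292 | 0.3 | 75.4% | 60.4% | 78.8% |
| | 0.5 | 74.1% | 69.6% | 84.1% |
| | 0.7 | 76.1% | 87.0% | 93.3% |

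- **Adjusted against follow-up only:** gains of about 3 points at 0.3, 9 to 10 at 0.5 and 17 to 18 at 0.7, in line with the formula.
- **Change scores:** 14 to 18 points worse than follow-up only at 0.3. At 0.5 they gain nothing for skewed data and lose about 5 points for ordinal data. At 0.7 they recover most of the loss: for skewed data at 40 per arm, (92.7 − 77.0) / (95.4 − 77.0) = 85%; for ordinal data, (84.5 − 74.2) / (92.6 − 74.2) = 56%.
- **Validity:** in a separate simulation with a skewed and a six-level ordinal outcome, all three tests had false-positive rates of about 5% (4 to 6%).

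**The case against.** The strongest objection is that the protocol names a test family in one sentence and leaves the tested quantity and any adjustment open. Those details often sit in a statistical analysis plan, which is not shown here. This stands in part. The silence on detail is not itself a fault. But the protocol does fix the test, and an analysis plan that follows it to the letter starts from a method without a covariate.

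Several stronger readings are tempting, and the documents do not support them:

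- **That the rank test cannot use the baseline.** It can be run on change scores or on baseline-adjusted residuals. At ρ = 0.5 the residual version reached 84.9% and 86.8% for skewed data at 40 and 292 per arm, close to rank ANCOVA. The protocol does not ask for it, but does not exclude it.
- **That this trial loses 10 points of power.** That figure needs ρ = 0.5, an 80% starting point and follow-up-only testing. The 80% and the 292 belong to a previous study's complication endpoint. The 40 per arm belongs to the nutrition variables in the amendment. The trial's own power calculation is deferred to the observational study.
- **That the patient-reported outcomes as a group fall under this rule.** The protocol does not classify ADL-staircase or QLQ-C30 as ordinal, or PASE or chair stands as skewed. Any that are treated as normally distributed go to repeated-measures ANOVA.
- **That visits would be pooled as independent observations, or stratification ignored.** Nothing in the text suggests the first, and no stratification variable has been adopted yet.

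It is also fair to say that the simulated gains are for rank ANCOVA. The proportional-odds model was not simulated.

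**Conclusion.** The point holds as a minor one about precision. For ordinal and skewed outcomes with a baseline, the named test takes no baseline covariate, and a baseline-adjusted comparison would be more powerful in the same patients. The gain is about 4, 10 and 18 points at correlations of 0.3, 0.5 and 0.7, on condition that follow-up values alone are tested and that this analysis has 80% power. None of these conditions is stated in the protocol. Change scores are not a dependable substitute, because their performance depends on a correlation that is not known in advance.

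A reader might infer that the planned comparison is biased or invalid. It is not: the rank test keeps its error rate under randomisation. Nor does the point reach length of stay, complications, mortality or discharge destination, which have no baseline to adjust for.

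**What to change.** Revise the rank-test rule in the intervention-study analysis paragraph (2:4) along these lines:

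- For ordinal or skewed outcomes with a baseline value, compare the arms at each named follow-up visit with a baseline-adjusted method: rank ANCOVA, or a proportional-odds model for ordinal scales. Terms: arm, baseline value, and any stratification variable if one is adopted.
- Keep the Wilcoxon rank-sum test for ordinal or skewed outcomes without a baseline, or as a supporting analysis. Name it as rank-sum so that it is not read as signed-rank.
- State how a missing baseline value is handled. The baseline questionnaires come by mail, so also state that they are to be completed before allocation is known.

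The cost is a few sentences. No patients, visits or data are added, and both methods can be run in SPSS, the software the protocol names. The downside is small: the proportional-odds assumption has to be checked, and missing baselines need a simple rule.

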3:6 What financial compensation or other benefits are provided to the research persons who participate in the project, and when is it paid?

No patient fee is paid by the participants in the intervention group, otherwise no financial compensation is provided.

4. Information and consent

4:1 The procedure for and the content of the information delivered to the patients at recruitment

Oral information is given in relation to recruitment for the study, if the patient is interested in participating, a written information paper will be provided. Thereafter, the patient will be contacted by the person responsible of recruitment and asked for participation. The information contain information regarding the content and procedure of the study, the research persons are also informed that they can cancel their participation at any time during the study without giving a reason or that it will affect their further care and rehabilitation. Patients who accept participation will be contacted by a physiotherapist to schedule the first assessment.

4:2 How and from who is content collected?

Written informed consent from the research person will be collected at the first assessment by the physiotherapist.

5. Ethical considerations

5:1 Describe all risks anticipated with participation

The physical assessments that will be conducted within the research project are frequently used in clinical practice, well established nationally and internationally, and do not provide any obvious risks for the participants. The choice to perform the exercise in the participants home might be perceived as an intrusion in the private sphere, however it is considered to have a small ethical impact. The value of exercising in the home setting and not having to transport themselves to a clinical is thought to outweigh possible perceptions of an intrusion in the private sphere. In frail older people physical exercise could be a risk for the individual, however previous studies have shown that the risk is small. The risk with physical inactivity is considered to be equal or higher. Close collaboration with physicians at the participating clinics will decrease the risk further.

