If this supplement in the study shows a positive effect, this additional application can lead to increased collaboration between dieticians and physiotherapists in both open and inpatient care with a strengthened care chain, improved care and, above all, improved care for frail older patients undergoing advanced surgery.

Ethical considerations: The original study is approved by the Regional Ethics Board in Stockholm (Dnr 2015/1179-31), but an additional application is needed for the specific nutrition intervention. Study patients will receive oral and written information in accordance with the original study and informed consent will be obtained before inclusion. Selected methods and measuring instruments are validated and used in similar studies in other patient groups.

4.

Overview of topic

Previous studies indicate that optimization of physical function and nutritional status before surgery can reduce the risk of complications. Patients would like to have their surgery completed as soon as possible and the standardized care processes that are now being introduced in Sweden within cancer care decreases the time for optimization. Until now, there are no medical indications that a waiting period of 3-4 weeks instead of 2-3 weeks implies poorer cancer-related outcomes.

Purpose

The study aims to describe patients' view of postponing the operation a couple of weeks in order to be able to improve their physical function and nutritional status prior to surgery.

Method

Approximately 20-30 patients who meet the criteria for inclusion in the on-going observational study will be asked about participation (Dnr 2015/1179-31). Oral and written information are provided by the research nurse, and written consent is obtained from the physiotherapist. Both those who are included in and declines participation in the observation will be approached. The interviews will take place before the surgery. All interviews will be recorded with a dictaphone. Recorded interviews will be transcribed and analyzed using an appropriate method. A code list of participants will be created and the list will be stored separate from the voice recordings and transcripts. Only the study leader has access to the code list.

Ethical considerations

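### The randomised trial sets a two-week minimum intervention, but its written eligibility criteria do not require two weeks before surgery

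*Protocol*

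**What the plan says.** Protocol section 2:4 (Intervention study) ties the length of the programme to the wait for surgery and sets a floor: "The intervention period will differ depending on individual variations in preoperative waiting time", but "the intervention time will be a minimum of two weeks". It also says that "the randomization will be conducted after the baseline assessments", and it schedules a second round of physical tests "after the intervention but before surgery".

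Section 3:1 (Intervention study) gives the entry rules. Inclusion needs age over 70 and command of Swedish, with further inclusion criteria to come from the observational study. Exclusion is for a health status that rules out the physical tests, "or a need of acute surgery within 7 days". No other eligibility rule refers to time.

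Section 4:1 describes the steps before entry: oral information, then written information, then a contact asking for participation. After that, "Patients who accept participation will be contacted by a physiotherapist to schedule the first assessment". Section 4:2 places written consent at that first assessment. The statistical paragraph of 2:4 specifies an intention-to-treat comparison.

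Part 4 of the amendment, which introduces an interview study, remarks that "the standardized care processes that are now being introduced in Sweden within cancer care decreases the time for optimization" and that "there are no medical indications that a waiting period of 3-4 weeks instead of 2-3 weeks implies poorer cancer-related outcomes".

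**The concern.** The two sections give different answers to who may be randomised. Section 2:4 implies that everyone allocated to exercise has at least 14 days available. The list in 3:1, applied as written, admits people who do not.

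Two things could follow. If staff apply 3:1 literally, some patients are randomised who could never have received the stated minimum. Intention-to-treat rightly keeps them in the comparison, where they pull the estimated effect towards no difference if a shorter programme works less well. If staff instead apply the two-week floor informally, entry depends on individual judgement about the surgery date, and the protocol does not define the randomised population in a way that others could reproduce.

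**Working it through.** No power or sample-size figure is involved. The check sets the rules side by side.

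**Inputs**
- Minimum intervention time: two weeks, or 14 days (2:4).
- Only timing rule for entry: exclusion if acute surgery is needed within 7 days (3:1).
- Order of events: information, contact, scheduling, consent and baseline tests, then randomisation (4:1, 4:2 and 2:4).

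Days are counted here from randomisation. The protocol does not say where the 7 days start. If they start at the first surgical visit, fewer days remain after randomisation, so this count is the lenient one.

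**Step 1: apply 3:1 as written**

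| Surgery | Excluded by 3:1? | Can receive 14 days? |
|---|---|---|
| Acute, days 1–7 | Yes | No |
| Acute, days 8–13 | No | No |
| Planned, before day 14 | No | No |
| Any, day 14 or later | No | Yes |

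The middle two rows are the gap. For acute surgery the shortfall between the rules is 14 − 7 = 7 days. For planned surgery 3:1 has no time limit at all.

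**Step 2: look for another step that closes the gap**
- Section 2:7 makes surgeons responsible for applying the exclusion criteria, but those contain only the 7-day rule.
- Sections 4:1 and 4:2 (contact, scheduling, consent) mention no check of the surgery date.
- Section 2:4 gives randomisation to the responsible researcher, without a date check.
- Postponing surgery appears only as the topic of the interview study in amendment part 4. It is not a procedure of the randomised trial.

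No step closes it.

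**Step 3: ask whether short intervals are plausible**

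Recruitment is consecutive from the first surgical visit (3:1). Amendment part 4 mentions waits of 2–3 weeks, without defining their start. Assume that they run from the first visit and that d days pass before randomisation. Days left = W − d, where W is the wait:

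| Assumed d | W = 14 | W = 21 |
|---|---|---|
| 3 | 11 | 18 |
| 5 | 9 | 16 |
| 7 | 7 | 14 |

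On that assumption a two-week wait leaves no slack (14 − 14 = 0 days) and a three-week wait leaves 21 − 14 = 7 days. A later start of the wait gives more slack. The table shows only that the gap could be reached in practice, since both the start and d are assumed.

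**Step 4: size of the effect**

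Dilution would depend on the share of patients with under 14 days and on how much benefit a shortened programme keeps. The protocol gives neither, and it defers the power calculation for the randomised trial (3:3). No figure can be derived.

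**The case against.** The best defence is that 2:4 states its floor without qualification. Read as a whole, the protocol then does not allow someone known to have under two weeks to be enrolled, and all that is missing is a repetition in 3:1. The 7-day rule also concerns clinical urgency and was never offered as a minimum wait for elective patients. The eligibility list is openly unfinished, and a feasibility study comes before the trial (amendment part 1).

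Much of this stands. The floor may well be meant as an entry condition, and a waiting-time criterion could still be added. Two points remain. The same sentence of 2:4 lets duration follow the wait, and nobody is told to apply the floor at screening. The criteria still to come are to be based on the observational results, and waiting time is not named among them.

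A reader might go further and infer that many patients will have too little time. The documents do not support this. The shortest wait mentioned is two weeks, in a passage about cancer care written for a separate interview study. A reader might also infer a definite loss of power or a need for a larger sample. Any such figure would rest wholly on assumed shares and an assumed dose-response relation. Some variation in dose is part of the design, because 2:4 deliberately lets duration vary.

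**Conclusion.** The point holds as an internal inconsistency. The eligibility list in 3:1 does not carry the two-week minimum of 2:4, so patients with planned surgery before day 14, or acute surgery on days 8 to 13, meet the written criteria without being able to receive the programme as specified. The effect is likely to be modest and cannot be quantified from the protocol.

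The conclusion rests on the wording of the two sections and on the absence of any date check between them. It does not depend on how common short waits are. It would fall away if a waiting-time criterion were added when the inclusion criteria are completed. It is still worth correcting: a cut-off that admits patients who breach another stated rule is more than a missing detail, and the plan has already chosen the two-week floor.

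**What to change.** - In 3:1 (Intervention study), add that surgery, whether planned or acute, is expected at least 14 days after randomisation, matching the minimum in 2:4.
- Have the randomising researcher check and record the booked or expected surgery date before allocation, so that the rule works identically for both arms.
- State that patients whose surgery is brought forward after randomisation remain in the intention-to-treat analysis.

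The date should also leave room for the tests between the intervention and surgery. The interval from assessment to surgery in the 200 observational patients is a poor guide to the time available, because 2:4 says only that they are assessed preoperatively and fixes no day.

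The cost is one eligibility line and one recorded date. Recruitment will be somewhat slower, and the results will apply to patients with at least two weeks to wait. The plan's own minimum already implies that restriction.
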